## **4. STUDY PLAN AND TIMING OF PROCEDURES**

The Study Plan and schedule of assessments is provided in [Table 1](#).

Details of study assessments completed during the Screening, Treatment, and Follow-up periods are included in sections 4.1, 4.2, and 4.3.

**Table 1 Study Plan and Schedule of Assessments**

Study Period / Visit	Screening	ILR Insertion by EP cardiologist	Baseline/ Randomization	New Dialysate Accommodation Period 1	Treatment Phase 1	Cross-over	New Dialysate Accommodation Period 2	Treatment Phase 2	ILR Removal by EP cardiologist	End of Study	Reference to Protocol Section
Study Week (Wk) [* , ** or ***]	-4 to -3**	-2*	1**	1 & 2**	3 to 10**	11**	11 & 12**	13 to 20**	21-22*	22-23***	
Study Day (D)	-28 to -15	-14	1	1 to 14	15 to 70	71	71 to 84	85 to 140	Between D141 and D155	Within 1 to 14 days after ILR Removal	
Day of the week			M/T	M/T	M/T	M/T	M/T	M/T			
Written informed consent	X										4.1.1
Assignment of unique Screening Number	X										4.1.2
Demographics	X										4.1.3
Medical/surgical & Medication history	X										4.1.4
Physical examination	X										4.1.5
Vital signs and weight measurements	X			X	X		X	X		X	4.1.6
12-lead ECG	X										5.2.3.1
K+ Piccolo POCT (pre-dialysis) [1]	X			X	X		X	X			4.1.7 4.2.1

**Table 1 Study Plan and Schedule of Assessments**

Study Period / Visit	Screening	ILR Insertion by EP cardiologist	Baseline/ Randomization	New Dialysate Accommodation Period 1	Treatment Phase 1	Cross-over	New Dialysate Accommodation Period 2	Treatment Phase 2	ILR Removal by EP cardiologist	End of Study	Reference to Protocol Section
Study Week (Wk) [* , ** or ***]	-4 to -3**	-2*	1**	1 & 2**	3 to 10**	11**	11 & 12**	13 to 20**	21-22*	22-23***	
Study Day (D)	-28 to -15	-14	1	1 to 14	15 to 70	71	71 to 84	85 to 140	Between D141 and D155	Within 1 to 14 days after ILR Removal	
Inclusion/exclusion criteria	X		X								3.1, 3.2
Day of the Week			M/T	M/T	M/T	M/T	M/T	M/T			
ILR insertion [7]		X									4.1.9
Randomization to one of two treatment sequences [6]			X								3.5
Study drug dispensed/ returned on 3.0 K+/2.5 Ca++ dialysate group				X	X		X	X			7.2.2
Cardiac Data Loop Recordings					X			X			4.2.2
K+, Ca++ and PO 4 Piccolo POCT promptly before dialysis end) [2]				X	X		X	X			4.2.1

**Table 1 Study Plan and Schedule of Assessments**

Study Period / Visit	Screening	ILR Insertion by EP cardiologist	Baseline/ Randomization	New Dialysate Accommodation Period 1	Treatment Phase 1	Cross-over	New Dialysate Accommodation Period 2	Treatment Phase 2	ILR Removal by EP cardiologist	End of Study	Reference to Protocol Section
Study Week (Wk) [* , ** or ***]	-4 to -3**	-2*	1**	1 & 2**	3 to 10**	11**	11 & 12**	13 to 20**	21-22*	22-23***	
Study Day (D)	-28 to -15	-14	1	1 to 14	15 to 70	71	71 to 84	85 to 140	Between D141 and D155	Within 1 to 14 days after ILR Removal	
Blood samples for PBUTs [3]					X						4.2.1
Day of the Week			M/T	M/T	M/T	M/T	M/T	M/T			
Local laboratory Mg ++ promptly before dialysis end) [4]				X	X		X	X			4.2.1
Adverse event recording & review [8]				X	X	X	X	X	X	X	6.4
Serious Adverse event recording & review [9]	X	X	X	X	X	X	X	X	X	X	6.4
Concomitant medication	X	X	X	X	X	X	X	X	X	X	5.2.5, 7.7
Local laboratory Mg ++ promptly before dialysis end) for muscle cramping [5]				X	X		X	X			4.2.1

**Table 1 Study Plan and Schedule of Assessments**

Study Period / Visit	Screening	ILR Insertion by EP cardiologist	Baseline/ Randomization	New Dialysate Accommodation Period 1	Treatment Phase 1	Cross-over	New Dialysate Accommodation Period 2	Treatment Phase 2	ILR Removal by EP cardiologist	End of Study	Reference to Protocol Section
Study Week (Wk) [* , ** or ***]	-4 to -3**	-2*	1**	1 & 2**	3 to 10**	11**	11 & 12**	13 to 20**	21-22*	22-23***	
Study Day (D)	-28 to -15	-14	1	1 to 14	15 to 70	71	71 to 84	85 to 140	Between D141 and D155	Within 1 to 14 days after ILR Removal	
Pregnancy Test for Females of Childbearing Potential	X										

Abbreviations: AE=adverse event; Ca=calcium; ECG=electrocardiogram; EP=electrophysiologist; ILR=insertable loop recorder; K=potassium; Mg++=magnesium; PBUTs=protein-bound uremic toxins [including p-Cresol sulfate [PCS], indoxyl sulfate, and asymmetric dimethylarginine [ADMA)]; SAE=serious adverse event

\*Performed on any day. (Note: ILR placement needs to be one week prior to baseline, which starts on Mondays or Tuesdays after each long dialysis weekend.)

\*\*Performed weekly, on Mondays or Tuesdays after each long dialysis weekend. (Note: Screening ICF can be obtained on any dialysis day, but all other procedures need to be performed on Monday or Tuesdays after the long dialysis weekend. Additionally, consenting may be conducted several weeks prior to other study procedures depending on the need for a prohibited medication washout or whether the consenting process occurred on a day other than the Monday or Tuesday after the long dialysis weekend.)

\*\*\*Performed on any dialysis day

[1] K+ Piccolo POCT (utilizing full renal panel) are performed pre-dialysis, on a Monday or Tuesday after the long dialysis weekend, twice during the Screening period, and weekly during the treatment period (both 2-week accommodation periods and 8-week Treatment phases). Note: K+ Piccolo POCT may be performed several weeks after consenting depending on the need for a prohibited medication washout or whether the consenting process occurred on a day other than the Monday or Tuesday after the long dialysis weekend.

[2] During the treatment period (both 2-week accommodation periods and 8-week Treatment phases), a second Piccolo POCT is performed promptly before dialysis end and within 30 minutes prior to rinse back on Mondays or Tuesdays after each long dialysis weekend (i.e., weekly), to measure K+, Ca++ and PO4.

[3] Applies only to the first twenty-five (25) patients randomized receiving standard treatment (hemodialysis using 2.0K+/2.5 Ca++ dialysate bath, without Lokelma supplementation) during Treatment Phase-1. Performed weekly, on Mondays or Tuesdays after each long dialysis weekend, promptly before dialysis end and within 30 minutes prior to rinse back.

[4] Performed weekly, on Mondays or Tuesdays after each long dialysis weekend, promptly before dialysis end and within 30 minutes prior to rinse back. Mg++ levels will be determined by the local laboratory at each site.

[5] Performed (if possible) upon symptomatic muscle cramping, promptly before dialysis end and within 30 minutes prior to rinse back. Mg++ levels will be determined by the local laboratory at each site.

[6] Baseline/Randomization is conducted on Week 1 of the new Dialysate Accommodation Period 1. Crossover occurs on the same day as Week 11 of the new Dialysate Accommodate Period 2. Neither Baseline/Randomization nor Crossover will be considered a separate visit.

[7] If ILR insertion is performed more than 30 days after the last K+ Piccolo POCT determination, please contact the sponsor who will determine if an additional K+ Piccolo POCT determination will be required prior to the baseline visit. These will be handled on a case-by-case basis.

[8] Adverse events will be collected from the time of first dose of Lokelmaâ, throughout the treatment and post-treatment follow-up period, up to the last study visit.

[9] SAEs will be reported from the time the patient signed the Informed Consent Form.

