## Study design

This is a prospective, open-labelled, randomized, 2x2 cross-over design study of 88 patients with end stage renal disease (ESRD) receiving routine out-patient dialysis using a standard 2.0 potassium ion ( $K^+$ )/2.5 calcium ion ( $Ca^{++}$ ) dialysate bath. The overall aim of the study is to determine whether converting stable hemodialysis patients from a “standard” 2.0  $K^+$ /2.5  $Ca^{++}$  dialysate (without Lokelma) to a 3.0  $K^+$ /2.5  $Ca^{++}$  mEq dialysate supplemented with the orally administered potassium binder sodium zirconium cyclosilicate (Lokelma®) to treat interdialytic hyperkalemia will reduce the incidence and duration of post-dialysis atrial fibrillation.

Following screening, eligible subjects will undergo placement of an implantable cardiac loop recorder (LINQ device) to monitor for the development of atrial fibrillation or any clinically significant cardiac arrhythmias [CSCA]). After a two-week recovery period (to allow the patient to heal from cardiac loop recorder placement), patients will be randomized (1:1 ratio) to one of two treatment sequences:

- Sequence **A**: standard 2.0  $K^+$ /2.5  $Ca^{++}$  dialysate with no Lokelma supplementation for two (2) months, followed by a cross-over to experimental 3.0  $K^+$ /2.5  $Ca^{++}$  dialysate with Lokelma supplementation (on off-dialysis days) for two (2) months;

Or

- Sequence **B**: experimental 3.0  $K^+$ /2.5  $Ca^{++}$  dialysate with Lokelma supplementation (on off-dialysis days) for two (2) months, followed by standard 2.0  $K^+$ /2.5  $Ca^{++}$  dialysate with no Lokelma supplementation for two (2) months.

Each two-month treatment period (both 2.0  $K^+$ /2.5  $Ca^{++}$  dialysate and 3.0  $K^+$ /2.5  $Ca^{++}$  dialysate with Lokelma sequences) will be preceded by a two-week run-in period, to allow the patient to adapt to the new dialysate bath.

While receiving the higher  $K^+$  dialysate, patient will be treated on off-dialysis days (4 days/week) with Lokelma, titrated to maintain  $K^+$  between 4.0 and 5.5 mEq/L. Refer to section 7.2 for the initial dose and frequency details.

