## Duration of treatment

Following the screening period’s two confirmatory pre-dialysis  $K^+$  measurements and after meeting study eligibility criteria, patients will be referred to the electrophysiology cardiologist of choice by the site principal investigator where a sub-cutaneous (SQ) continuous cardiac loop recorder will be placed in the left anterior chest wall. Patients will be allowed to accommodate to the loop recorder for 2-weeks before they are randomized (1:1 ratio) to one of two treatment sequences (Sequence A or B, as described above), and start study treatment with 2.0  $K^+$ /2.5 $Ca^{++}$  dialysate bath without potassium binder supplementation or 3.0  $K^+$ /2.5  $Ca^{++}$  dialysate bath with Lokelma supplementation (taken on off-dialysis days). There will be a **2-week** cardiac monitoring blanking period where patients will be allowed to accommodate to the higher  $K^+$  dialysate and the use of Lokelma. Any data recorded by the insertable loop recorder (ILR, LINQ device) during this time period will not be used for any endpoint analysis. During the next **8-week** treatment period (Phase I of the study), patients will undergo continuous cardiac monitoring by the ILR. At the end of Phase I, data will be downloaded from the ILR and a new **2-week** blanking period will begin where patients will “cross-over” to the alternative dialysate bath and will be allowed to equilibrate to the new dialysate. Patients dialyzed for 8 weeks using a 2.0  $K^+$ /2.5 $Ca^{++}$  bath (without potassium binder supplementation) during Phase I will be switched to the 3.0  $K^+$ /2.5  $Ca^{++}$  bath with Lokelma supplementation, and *vice versa*. During the subsequent **8-week** treatment period (Phase II of the study), patients will undergo continuous cardiac monitoring by the ILR. At the conclusion of Phase II, a new cardiac monitoring blanking period will begin and blood sampling will be stopped. The ILR will be removed by the affiliated electrophysiology cardiologist. This process may take an additional 2 weeks. Therefore, for each patient, the planned total study treatment duration will be **20 weeks**, and the total study participation will be approximately **25 weeks**.

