The study design also includes several measures aimed to minimize the risk of adverse experiences. Because patients with persistently high serum  $K^+$  after the long dialysis weekend are not likely to tolerate the move to a higher  $K^+$  dialysate, the enrollment criteria include a requirement for two (2) separate pre-dialysis measurements of serum  $K^+ < 6.5$  mEq/L. A two-week recovery period will allow patients to heal from cardiac loop recorder insertion before randomization. In addition, each two-month treatment period (both sequences) will be preceded by a two-week accommodation period, to allow the patient to adapt to the new dialysate bath. While receiving the higher  $K^+$  dialysate, patients will be treated on off-dialysis days (4 days/week) with oral Lokelma, to reduce interdialytic hyperkalemia. Lokelma will be titrated to maintain serum  $K^+$  levels within a safe range, between 4.0 and 5.5 mEq/L.

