## 1.4 Study Design

This is a prospective, open-labelled, randomized, 2x2 cross-over design study of 88 patients with end stage renal disease (ESRD) receiving routine out-patient dialysis using a standard 2.0 potassium ion ( $K^+$ )/2.5 calcium ion ( $Ca^{++}$ ) dialysate bath. The overall aim of the study is to determine whether converting stable hemodialysis patients from a “standard” 2.0  $K^+$ /2.5  $Ca^{++}$  dialysate to a 3.0  $K^+$ /2.5  $Ca^{++}$  mEq dialysate supplemented with the orally administered potassium binder sodium zirconium cyclosilicate (Lokelma®) to treat inter-dialytic hyperkalemia will reduce the incidence and duration of post-dialysis atrial fibrillation.

Following the screening period’s two confirmatory pre-dialysis  $K^+$  measurements and after meeting study eligibility criteria, subjects will undergo placement of an implantable cardiac loop recorder (LINQ device) to monitor for the development of atrial fibrillation or any CSCA. After a two-week recovery period (to allow the patient to heal from the cardiac loop recorder placement), patients will be randomized (1:1 ratio) to one of two treatment sequences:

- Sequence A: standard 2.0  $K^+$ /2.5  $Ca^{++}$  dialysate with no Lokelma supplementation for two (2) months, followed by a cross-over to experimental 3.0  $K^+$ /2.5  $Ca^{++}$  dialysate with Lokelma (on off-dialysis days) for two (2) months;

Or

[figure not shown]
- Sequence B: experimental 3.0  $K^+$ /2.5  $Ca^{++}$  dialysate with Lokelma supplementation (on off-dialysis days) for two (2) months, followed by standard 2.0  $K^+$ /2.5  $Ca^{++}$  dialysate with no Lokelma supplementation for two (2) months.

Each two-month treatment period (both 2.0  $K^+$ /2.5  $Ca^{++}$  dialysate and 3.0  $K^+$ /2.5  $Ca^{++}$  dialysate with Lokelma sequences) will be preceded by a two-week run-in period, to allow the patient to adapt to the new dialysate bath.

While receiving the higher  $K^+$  dialysate, patient will be treated on off-dialysis days (4 days/week) with Lokelma, titrated to maintain serum  $K^+$  between 4.0 and 5.5 mEq/L.

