### **Post-LINQ Device Insertion**

For 2 weeks after LINQ device insertion, patients will be given time to heal and adapt to the device. During this 2-week blanking period, the device will measure continuous cardiac data, but it will not be interrogated and will not be used for analysis. During this blanking period, Medtronic will train study staff on how to interrogate and transmit LINQ device data, which will be sent to the Medtronic Monitoring Service; refer to the data flow shown in Figure 9.

After the 2-week ILR post-insertion recovery period, patients will be randomized to one of two treatment sequences, as described in [Section 3.5](#). The day of randomization will be denoted as Study Day 1 and will also mark the start of Treatment Phase 1.

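### A Table 1 footnote asks for loop recorder placement one week before baseline, while the table's own Day -14 column and the body text give a two-week recovery

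*Protocol*

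**What the plan says.** Table 1 (Study Plan and Schedule of Assessments) places insertion in a column headed Week -2, Study Day -14, with Baseline/Randomization at Day 1. The asterisk on that column leads to a footnote allowing insertion on any day, with the note that "ILR placement needs to be one week prior to baseline, which starts on Mondays or Tuesdays after each long dialysis weekend".

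The body text gives two weeks each time:

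- Synopsis, Study design: "After a two-week recovery period (to allow the patient to heal from cardiac loop recorder placement), patients will be randomized".
- Synopsis, Duration of treatment: "Patients will be allowed to accommodate to the loop recorder for 2-weeks before they are randomized".
- Section 1.2: "A two-week recovery period will allow patients to heal from cardiac loop recorder insertion before randomization". The paragraph containing this opens with "The study design also includes several measures aimed to minimize the risk of adverse experiences".
- Section 1.4: "After a two-week recovery period (to allow the patient to heal from the cardiac loop recorder placement), patients will be randomized".
- Section 4.1.9, whose heading carries Week -2: "For 2 weeks after LINQ device insertion, patients will be given time to heal and adapt to the device", and then "After the 2-week ILR post-insertion recovery period, patients will be randomized to one of two treatment sequences".
- Section 4.2: patients go to their allocated bath after the two-week post-insertion blanking period is complete.

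**The concern.** Sections 4.1 and 4.2 send sites to Table 1 for the timing of assessments, so a footnote there is working text. A coordinator who books insertion from the footnote could leave about a week before Day 1 and believe the visit is on schedule. A monitor reading Section 1.4 or 4.1.9 would record the same patient as a deviation.

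Three things are at stake.

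- **Participant protection.** Section 1.2 counts the recovery period among the measures that limit risk, and Section 1.3 names local chest-wall infection from insertion as a study risk.
- **Site conduct.** There is no single interval against which to judge a deviation. Section 4.1.9 also assigns training of study staff on device interrogation to this same two-week period.
- **Attribution of adverse events.** Section 8.5.6 starts the treatment-emergent window at the first dose (3.0 K+ bath with Lokelma) or the first visit (2.0 K+ bath). A shorter gap moves some late device complications past that point.

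**Working it through.** No sample-size or power figure is involved. The check compares the passages and counts days.

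**1. Do the two statements describe the same gap?** Footnote [6] to Table 1 places baseline and randomization together at Week 1, and Section 4.1.9 makes the day of randomization Study Day 1. An interval before baseline is therefore an interval before randomization.

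**2. Length of the gap** (numbering without a Day 0)

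| Source | Insertion | Gap to Day 1 |
|---|---|---|
| Table 1, Study Day row | Day -14 | 14 days (15 if a Day 0 is counted) |
| Synopsis, 1.2, 1.4, 4.1.9, 4.2 | two weeks before | 14 days |
| Table 1, * footnote | one week before, about Day -7 | about 7 days |

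The difference is 14 - 7 = 7 days, and 7/14 = 50% of the stated recovery.

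**3. Exact or minimum?** If the footnote means exactly one week, it cannot be met together with two weeks. If it means at least one week, 14 days satisfies both texts, but 7 days satisfies the footnote alone. On either reading the footnote accepts a gap that the body text does not.

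**4. Does another provision explain the difference?** The 30-day allowance in Section 4.1.9 and footnote [7] runs from the last potassium measurement to insertion, not from insertion to baseline. No passage provides for a shortened recovery.

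**5. Effect on analysed recordings.** Sections 4.1.9 and 4.2.2 exclude recordings from the post-insertion and accommodation periods. Treatment Phase 1 starts at Day 15. From insertion to the first analysed day:

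- two-week gap: 14 + 14 = 28 days, about 4 weeks;
- one-week gap: 7 + 14 = 21 days, about 3 weeks.

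The analysed window, Days 15 to 70, is the same in both cases.

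**6. Effect on treatment-emergent status, by onset of a device complication after insertion**

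| Onset after insertion | 14-day gap | 7-day gap |
|---|---|---|
| before about day 7 | before Day 1 | before Day 1 |
| about day 7 to 14 | before Day 1 | after Day 1, can be treatment-emergent |
| after about day 14 | after Day 1 | after Day 1 |

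Only the middle row changes.

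**The case against.** The best defence is that the footnote is a scheduling tolerance. It explains why insertion may be on any day of Week -2 although baseline is tied to a Monday or Tuesday. If Week -1 is Days -7 to -1, Week -2 is Days -14 to -8, and insertion in that week leaves 8 to 14 days, which is at least about one week. This reading is plausible, and it means that a site can comply with both texts by inserting at Day -14. It does not remove the problem: the footnote does not call itself a minimum, and gaps of 7 or 8 days still fall short of the two weeks in the body.

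Several stronger readings are tempting and are not supported:

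- *A site must breach one text to follow the other.* True only if one week means exactly one week.
- *Insertion complications in general would be counted against the first bath.* Section 8.5.6 counts only events starting on or after first dose or first visit, so early complications stay outside the window under either interval. For serious events, Sections 6.4.3 and 6.4.4 record causality to study procedures separately. Randomization is 1:1, so such complications would be expected to arise about equally under each first bath.
- *Every patient would change bath while the wound heals.* Patients already on the 2.0 K+ bath who start on it are not switched at Day 1, and no passage says that a change of dialysate affects healing.
- *Every randomized patient is exposed.* Exclusion criteria 18 and 21 allow an existing device with enough battery life, and those patients need no insertion.
- *The arrhythmia endpoints are compromised.* The excluded recording periods rule this out.

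**Conclusion.** The inconsistency is real, in current text, and minor. Table 1's footnote accepts about 7 days between insertion and Day 1, where the column it annotates and the rest of the protocol give 14. The size is up to 7 days, or half of the stated recovery, for a newly implanted patient scheduled from the footnote. The documents do not show how many patients that would be.

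The consequences are confined to participant protection, uniform conduct and deviation assessment, and the classification of device complications with onset about 7 to 14 days after insertion. No rate of such complications is given, so their number cannot be estimated. Efficacy endpoints are not affected. This is a conflict between passages and not a questionable design choice, since the body text is consistent throughout.

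The day counts assume no Day 0. Counting one would lengthen the Day -14 gap by a day and change nothing else in the conclusion.

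**What to change.** Reconcile the * footnote, the Week -2/Day -14 column, the synopsis (Study design and Duration of treatment) and Sections 1.2, 1.4, 4.1.9 and 4.2 so that one insertion-to-randomization interval is stated throughout, and say whether it is a minimum. Which interval applies is for the sponsor to decide.

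The cost is small. If the body text stands, one footnote changes in an amendment. If the footnote stands, the Day -14 column and each of the listed passages must change, including the description of the recovery period in Section 1.2.

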## **4.1 Screening Period**

The process for identifying prospective study patients (pre-screening) is described in [Section 3.3](#).

Screening assessments will be carried out according to the schedule provided in [Table 1](#). The following section details the screening activities, starting with the consent process. During screening, consenting patients will be assessed to ensure that they meet all eligibility criteria. Patients who do not meet these criteria must not be randomized in the study.

